4.3.5. Safety Lead-in Analysis Set

The safety lead-in analysis set will consist of the first 45 subjects who are randomized to the study. Subjects will be classified according to the actual vaccine received. The first 45 subjects enrolled will be in the older age group of 11 to 17 years, inclusive.

Cellular mediated responses in this group following study vaccination will be analyzed if subjects contribute a baseline sample and the required post-vaccination sample (ie, Day 8) that has at least 85% recovery following peripheral blood mononuclear cell (PBMC) procedures. Similarly, cellular-mediated immunity of the optional substudy will occur in a subset of subjects who contribute to Day 85 and Day 113 samples and have a similar recovery of PBMCs.

4.4. Handling of Missing Data

Impute Missing Colonization Data

Colonization data will be presented in the listings as reported for subjects consented to substudy only. For summaries and analysis, the following conventions apply.

When only one day out of two days (Day 92 or Day 99) is missing:

- If Day 92 is negative but Day 99 is missing, Day 99 will be imputed as negative;
- If Day 92 is missing but Day 99 is negative, Day 92 will be imputed using fully conditional specification multiple imputation.
- If any day is positive, the remaining missing data will not be imputed.

When subjects drop out before they visit on Day 92 but consent to the substudy, i.e., all two days (Day 92 and Day 99) are missing:

- Status of being positive or negative for a given day will be imputed using fully conditional specification multiple imputation.

Multiple imputation method for missing binary outcome of colonization

Imputation of the missing binary variable of being a colonizer or non-colonizer will be done using fully conditional specification with a logistic model. The multiple imputation procedure and the analysis will be conducted in three separate steps: 1) Imputation 2) Analysis of imputed complete data sets 3) combination of results using Rubin's rule.

1. Imputation (using SAS PROC MI): Use the logistic method with age group as covariate to impute the missing colonization status of being positive or negative by treatment group. The FCS LOGISTIC statement will be used with a seed of 57808563. In this MI approach, SAS® procedure PROC MI performs MI by replacing each missing value with a set of plausible values by treatment group. The missing data will be filled in multiple times to generate multiple complete data sets. The number of imputed complete data sets will be 50.
2. Analysis of imputed complete data sets: imputed data sets will then be analyzed separately using the same method for the colonization endpoint as described in [Section 8.4.1](#).
3. Combination of estimates across imputed datasets (can be obtained using SAS PROC MIANALYZE): the results obtained from Step 2 (one for each imputation), which are difference in response proportion and its standard errors, will then be combined per Rubin's rule (t statistics and standard errors), p-values for combined t-statistics will be derived using Student's t distribution with error degrees of freedom.

Impute Missing Adverse Events/ Prior or Concomitant Medications

Data will be presented in the listings as reported. For summaries and analysis, the following conventions apply.

A. Incomplete Start Date:

Missing day and month

- If the year is the **same** as the year of the first dosing date, then the day and month of the first dosing date will be assigned to the missing fields.
- If the year is **prior to** the year of first dosing date, then December 31 will be assigned to the missing fields.
- If the year is **after** the year of first dosing, then January 1 will be assigned to the missing fields.

Missing day only

- If the month and year are the **same** as the year and month of first dosing date, then the first dosing date will be assigned to the missing day.
- If either the year of the partial date is **before** the year of the first dosing date or the years of the partial date and the first dosing date are the same but the month of partial date is **before** the month of the first dosing date, then the last day of the month will be assigned to the missing day.
- If either the year of the partial date is **after** the year of the first dosing date or the years of the partial date and the first dosing date are the same but the month of partial date is **after** the month of the first dosing date, then the first day of the month will be assigned to the missing day.
- If the stop date is not missing, and the imputed start date is after the stop date, the start date will be imputed by the stop date, i.e. set to the stop date.

Missing day, month, and year

- No imputation is needed; the corresponding AE will be included as TEAE if the end date of the AE is after the first dose date or the end date is also missing.

B. Incomplete End Date:

If the imputed stop date is before the start date, then the imputed stop date will be equal to the start date.

Missing day and month

- If the year of the incomplete stop date is the **same** as the year of the last dosing date, then the day and month of the last dosing date will be assigned to the missing fields.
- If the year of the incomplete stop date is **prior to** the year of the last dosing date, then December 31 will be assigned to the missing fields.
- If the year of the incomplete stop date is **prior to** the year of the last dosing date but is the same as the year of the first dosing date, then the first dosing date will be assigned to the missing date.
- If the year of the incomplete stop date is **after** the year of the last dosing date, then January 1 or EOS date which ever occurred later will be assigned to the missing fields.

Missing day only

- If the month and year of the incomplete stop date are the **same** as the month and year of the last dosing date, then the day of the last dosing date will be assigned to the missing day.
- If either the year of the partial date is **not equal to** the year of the last dosing date or the years of the partial date and the last dosing date are the same but the month of partial date is **not equal to** the month of the last dosing date, then the last day of the month will be assigned to the missing day.

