There is an optional open-label substudy in which enrolled subjects may elect to participate at any time from the day of enrolment through Day 85. A separate signed ICF (and separate assent when necessary) will be obtained prior to participation in the substudy. Subjects will be excluded from participating in the substudy if they meet additional exclusion criteria listed in Protocol Section 4.1.2.1. Temporary vaccination holding criteria are to be followed for the Day 85 vaccination.

Up to 120 enrolled subjects may participate in the substudy. The duration of the entire study will not change; however, additional visits/procedures starting on Day 85 will include the following:

- 3 additional visits (Days 92, 99, and 113)
- 1 additional intranasal vaccination (Day 85)
- Up to 3 additional nasal samples, including 2 of those needed for midturbinate/nasopharyngeal sample collection (Days 92 and 99) and 1 needed for leukosorb (Day 113). Subjects will contribute to all Day 85 sampling (systemic and nasal).
- Up to 2 additional blood samples (Days 85, if not already assigned to provide, and 113, including blood for cellular-mediated and systemic immunity responses)
- 1 additional subject diary (subjects to record maximum daily reactogenicity [nasal/respiratory, systemic] in a subject diary for 7 consecutive days starting the day following study vaccination)
- 1 additional test for SARS-CoV-2 within 72 hours prior to Day 85 vaccination.

All subjects participating in the open-label substudy will receive an intranasal re-vaccination/attenuated challenge with BPZE1 on Day 85. Subjects may have the planned re-vaccination/attenuated challenge deferred to a later date (up to 20 days) if pre-defined temporary exclusion criteria in Protocol Section 4.1.2.1 are met or for other personal reasons (eg, holiday, school schedule). Subjects will be monitored for at least 30 minutes after re-vaccination/attenuated challenge, with a post-vaccination evaluation for reactogenicity (nasal/respiratory, and systemic) completed prior to release from clinical observation.

Subjects will receive a subject diary on Day 85. All subjects (with assistance when needed) will record maximum daily reactogenicity in a subject diary for 7 consecutive days starting the day following re-vaccination/attenuated challenge (retrospective of the highest value in the previous 24 hours).

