4.2. Randomization, Stratification, and Blinding

Subjects will be randomly assigned to 1 of 3 treatment groups, in a 1:1:1 ratio, as presented in [Table 3-1](#). Enrolment will be operationally managed at the study level to maintain a minimum number of subjects enrolled in 2 age groups: 6 to 10 years, inclusive; and 11 to 17 years, inclusive. Subjects will be operationally managed to maintain a minimum number of subjects enrolled in 2 age groups. A staggered enrolment is planned: the first 45 subjects enrolled will be in the older age group of 11 to 17 years, inclusive, and designated the safety lead-in cohort.

Enrolled subjects may participate in an optional substudy in which subjects may elect to participate at any time from the day of enrolment through Day 85. No randomization is planned for the substudy as all subjects participating in the open-label substudy will receive an intranasal re-vaccination/attenuated challenge with BPZE1 on Day 85.

Biostatistics will generate the randomization schedule using SAS® software Version 9.4 or later (SAS Institute Inc, Cary, North Carolina) for the interactive response technology, which will link sequential subject randomization numbers to treatment codes. The randomization schedule will

be created by the dedicated randomization team, stored in a separate project area, and will be blinded to the project team with the exception of an unblinded team who will manage vaccine logistics, preparation, and administration, but will not be involved in study-related assessments or have subject contact for data collection following study vaccination.

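### The colonisation imputation in SAP 4.4 has no guard against separation: in an arm-by-age cell with no (or only) colonised children it can impute the opposite status far too often

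*SAP*

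**What the plan says.** Step 1 of the multiple imputation in SAP 4.4 reads: "Use the logistic method with age group as covariate to impute the missing colonization status of being positive or negative by treatment group". On the procedure it adds "The FCS LOGISTIC statement will be used with a seed of 57808563" and "The number of imputed complete data sets will be 50". It mentions no augmented or penalised likelihood, and no rule for a cell or arm in which every observed child has the same status.

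Only two kinds of substudy child reach the model:

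- Both days missing: "Status of being positive or negative for a given day will be imputed using fully conditional specification multiple imputation".
- Day 92 missing with a negative Day 99: "If Day 92 is missing but Day 99 is negative, Day 92 will be imputed using fully conditional specification multiple imputation".

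The reverse pattern is handled by rule ("If Day 92 is negative but Day 99 is missing, Day 99 will be imputed as negative"), and one positive day stops any further imputation. Step 3 combines differences in proportions by Rubin's rule. No pooling of the relative risk or the RRR is described.

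On cell sizes, SAP 4.2 names "2 age groups: 6 to 10 years, inclusive; and 11 to 17 years, inclusive" and SAP 3.1 says "Up to 120 enrolled subjects may participate in the substudy". Joining is voluntary and there is no quota per arm.

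On analysis sets, SAP 8.4.1 bases the colonisation analysis on the per-protocol set, with the Immunogenicity Analysis Set as a sensitivity analysis. SAP 4.3.4 takes missing Day 92 and Day 99 cultures out of the colonisation endpoint in the per-protocol set. SAP 4.4 states its conventions without limiting them to either set.

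**The concern.** A logistic model with age group as covariate, fitted within one arm, has no finite maximum-likelihood estimate when one age cell is all negative or all positive. The fitted linear predictor drifts toward minus or plus infinity and its standard error grows much faster. Proper imputation draws the coefficients from a normal distribution with that enormous spread, so the drawn probability in the cell is close to 0 in some imputations and close to 1 in others. The data in the cell all point one way, yet the imputed values are close to a coin toss.

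The situation is foreseeable. Protocol 1.1 reports that in adults BPZE1-induced mucosal immunity, unlike Boostrix, was associated with protection from colonisation, and SAP 2.3.3 hopes to show the same here. A BPZE1 cell with no colonised child is therefore close to the result the substudy wants. The imputation would then raise the BPZE1 rate, or lower the rate of a fully colonised control cell. Either error pulls the arms together and adds between-imputation variance. SAP 8.4.1 attaches a success criterion to an RRR above 0%.

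**Working it through.** The plan gives no power, expected rate or expected missingness for colonisation, so there is no stated figure to reproduce.

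**Inputs**

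- From SAP 4.4: model, covariate, imputation within arm, 50 imputations.
- From SAP 3.1 and 4.2: up to 120 children, three arms, two age groups.
- Assumed: an even split, so 120/3 = 40 per arm and 40/2 = 20 per cell.
- Assumed: about 10% missing, borrowed from the main-study dropout figure in SAP 4.1. That is 2 missing and 18 observed per cell.
- Assumed: BPZE1 colonisation 2-50%, control 50-95%.

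**1. Chance of an empty cell.** With true rate c, P(0 of 18) = (1 - c)^18. Exactly one of an arm's two cells is empty with probability 2p(1 - p), where p is that value. For at least one of the two BPZE1 arms, it is 1 - (1 - that)^2.

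| c | 0/18 in a cell | exactly one cell of an arm | at least one of two BPZE1 arms |
|---|---|---|---|
| 5% | 0.397 | 0.479 | 0.728 |
| 10% | 0.150 | 0.255 | 0.445 |
| 20% | 0.018 | 0.035 | 0.070 |

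The per-cell and per-arm figures also apply to all-colonised cells in a control arm at 95%, 90% and 80%. If both cells of an arm are empty (2.3% of arms at c = 10%, 15.8% at 5%), the outcome has a single level and the model cannot be fitted, which is a separate failure.

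**2. What the model imputes in the empty cell.** Status was regressed on age group by maximum likelihood, coefficients were drawn from the normal approximation, and the missing children were then imputed. With 0/18 in the cell, the share imputed colonised depends on when the fit stops:

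| iterations | 5 | 8 | 10 | 12 | 15 | 20 |
|---|---|---|---|---|---|---|
| share | 0.13 | 0.35 | 0.43 | 0.47 | 0.49 | 0.50 |

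At convergence the linear predictor is about -20 with SD in the thousands, and the share is 0.50 whether the other cell holds 1, 2, 4 or 8 of 18. Across 8 to 25 observed children per cell, the share is 0.33-0.50 at 8 or more iterations. With 18/18 colonised, the mirror result is 0.50 imputed non-colonised.

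**3. By day.** With only Day 92 missing, a two-day version gave 0.47-0.51. With both days missing and each imputed separately, the either-day share was 0.72-0.82, in line with 1 - 0.5^2 = 0.75.

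**4. With augmentation.** Pseudo-observations of total weight 2 give a linear predictor of -3.6 (SD 1.4) and a share of 5.7%.

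**5. Effect on the arm.** Take 2/18 and 0/18 observed, with 2 missing per cell. The observed rate is 2/36 = 5.6%. The other cell adds 2 × 2/18 = 0.222 expected positives.

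- Share 0.50: (2 + 0.222 + 1.0)/40 = 8.1%.
- Share 0.75: (2 + 0.222 + 1.5)/40 = 9.3%.
- Share 0.35: (2 + 0.222 + 0.7)/40 = 7.3%.
- Augmented fit: about 6.0%.

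RRR = 1 - (BPZE1 rate)/(control rate):

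| control rate | observed | share 0.50 | share 0.75 | augmented |
|---|---|---|---|---|
| 80% | 93.1% | 89.9% | 88.3% | 92.5% |
| 50% | 88.9% | 83.9% | 81.4% | 87.9% |

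With 4 missing per cell (16 observed) and share 0.50, the arm rate goes from 6.2% to 11.3%, and the RRR from 92.2% to 85.9% (80% control) or from 87.5% to 77.5% (50% control).

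**6. Variance.** Both missing children in the empty cell switch together, so at share 0.50 the arm rate jumps by 2/40 = 0.05 between imputations. That contributes (1 + 1/50) × 0.05^2 × 0.5 × 0.5 = 0.00064, against a within-imputation variance of 0.081 × 0.919/40 = 0.00186. This one cell adds about a third.

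**The case against.** The strongest objection is that imputed values may never enter the main analysis. SAP 4.3.4 removes missing cultures from the per-protocol endpoint, and 8.4.1 makes that set the main one. This stands. A reader might infer that the headline rates and RRR are distorted, but on the wording of 4.3.4 they need not be. What remains is the Immunogenicity Analysis Set sensitivity analysis, to which 4.3.4's removal rule does not apply.

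Second, a reader might infer that half the missing children are always given the wrong status. The documents do not support that. The share depends on the stopping rule and on whether one or both days are missing. The figures come from a direct implementation of the stated model, not from SAS output. True status is unknown, so the most that can be said is that the imputed status is opposite to that of every observed child in the cell.

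Third, the success decision is unlikely to turn on this. BPZE1 cells separate when few children are colonised, so the contrast with control is large. In a heavy case (6 missing per cell, 50% control), setting all 6 in the empty cell to colonised gives about 9/40 against 20/40. The relative risk is 0.45, with an approximate Wald interval of 0.23-0.87 (SE of the log = √(1/9 - 1/40 + 1/20 - 1/40) = 0.333). The RRR lower limit, 13%, stays above zero. This single-data-set interval omits between-imputation variance, but the direction of the argument is sound.

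Fourth, step 3 pools the difference in proportions, so no pooled RRR exists to be biased. That is correct. The pooled difference still uses the same imputed rates and is pulled toward zero.

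Finally, the even split, the colonisation rates and the missingness are assumptions, and the cell must also contain a missing child. None of this removes the defect: the stated rule performs badly in a foreseeable data pattern, and nothing in the plan catches it.

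**Conclusion.** The point holds in a conditional form. SAP 4.4 followed as written, with an unaugmented fit run near convergence, imputes the status opposite to every observed child in a separated cell in roughly 35-50% of imputations, less if the fit stops very early. The either-day figure is 72-82% when both days are missing and imputed separately. An augmented likelihood gives about 6%. Separation is plausible if colonisation is about 10% or less in a BPZE1 arm, or about 90% or more in the control arm.

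With about 2 missing children per cell, the arm rate shifts by about 2-4 percentage points. The RRR within imputed data sets shifts by about 3-8 points for shares of 0.50-0.75, and by about 2-3.5 points at 0.35. The pooled difference shrinks and between-imputation variance rises. Heavier missingness enlarges all of these.

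The reach is whichever analysis uses the imputed data. Unless the conflict between 4.3.4 and 4.4 is resolved in favour of imputation, that is only the sensitivity analysis in 8.4.1. There the artefact could make a sound result look fragile. The documents do not support a claim that the main result is biased or that the success decision would reverse. The change should still be made, because it is cheap and the failure arises in the very scenario the substudy hopes for.

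**What to change.** Make three changes to the SAP before database lock:

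1. In 4.4 step 1, specify an augmented likelihood for the FCS LOGISTIC imputation (LIKELIHOOD=AUGMENT), or an equivalent penalised likelihood.
2. Add a fallback for an arm in which all observed children have the same status. The augmentation option alone has not been shown to handle that case.
3. Reconcile 4.3.4 with 4.4: state for each analysis set whether missing Day 92 and Day 99 cultures are removed or imputed.

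The cost is one option in the code and a few sentences, with no new data and no change in sample size. The downside is a slight shrinkage of imputed probabilities toward 0.5: in the worked arm, about 6.0% against 5.6% observed. Settling this before lock also avoids choosing a remedy after the separated cell has been seen.

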4.3.4. Per-Protocol (PP) Immunogenicity Analysis Set

Immunogenicity Analyses to be performed based on PP Immunogenicity Analysis Set.

The PP immunogenicity analysis set will consist of all subjects in the immunogenicity analysis set, with the following exclusions:

- Data from all available visits for subjects following the receipt of unsuitable investigational product (either via dispensed and/or assigned or delivered).
- Data from all available visits for subjects found to be ineligible at baseline per protocol.
- Data from all subjects who received at least one dose of whole-cell pertussis (wP) containing vaccine in their life.
- Data from all available visits for subjects following the use of major immune modulators or immunosuppressants or following the receipt of blood products.
- Data from all available visits for subjects following clinically significant protocol deviations that can affect the efficacy (immunogenicity) results as determined by clinical review.

- Data from any visit that occurs substantially out of window as defined by exceeding 30 days past the visit window or the time point whereby the follow-up visit should have occurred, whichever is most restrictive.
- For subjects in the colonization substudy, missing Day 92 and Day 99 cultures will be removed from the Colonization endpoint.

For analyses using the PP immunogenicity analysis set, subjects will be classified according to the randomized treatment group. Determination of exclusions from the PP Immunogenicity Analysis Set will be performed by the sponsor clinical lead in a blinded fashion prior to the database lock.

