4.5. Analysis Window/Visit

Visit windows for each visit are defined in [Section 13.1](#). Additionally, analysis windows will be derived using below rules:

Study Visit/Study Day	Main Study	Substudy
Visit 1/Day 1	Day 1	
Visit S1/Day 8 ^a	Day 6 to Day 18	
Visit 2/Day 29	Day 19 to Day 57	
Visit 3/Day 85	Day 58 to Day 127	Day 58 to Day 115
SS Visit 4 ^b /Day 92	N/A	3 days before SS Visit 4 to 4 days after SS Visit 4

SS Visit 5 ^b /Day 99	N/A	3 days before SS Visit 5 to 7 days after SS Visit 5
SS Visit 6 ^b /Day 113	N/A	7 days before SS Visit 6 to 28 days after SS Visit 6
EOS/Day 169	Day 128 to Day 199	29 days after SS Visit 6 to Day 199

^a Safety Lead-in subject only

^b Subjects in substudy only

5. Subject Disposition

The number of subjects who were randomized and eligibility criteria met/failed will be summarized based on all enrolled subjects. Eligibility criteria met/failed will be listed based on all screened subjects.

Disposition of all enrolled subjects will be summarized by treatment groups, age groups (6 - 10 years, and 11 – 17 years, and 10 – 17 years) and overall including:

- Number screened
- Number screen failures
- Number of subjects randomized
- Number of subjects randomized, not vaccinated
- Number of subjects vaccinated
- Safety Analysis Set
- ITT Analysis Set
- Immunogenicity Analysis Set
- Per Protocol Immunogenicity Analysis Set
- Safety Lead-in Analysis Set
- Number of subjects who participated in substudy
- Number of subjects who completed substudy
- Number of subjects who completed study (EOS Visit)
- Number of subjects who prematurely discontinued study
- Primary reason for premature discontinuation of study

Primary reasons for study discontinuation collected on the Study Termination eCRF will be summarized with the following categories:

- Adverse Event

- Lost to Follow-Up
- Withdrawal of Consent
- Investigator Decision
- Sponsor Decision
- Death
- Other

A by subject listing will be provided based on the ITT Analysis set, subjects who are willing to participate in the substudy will also be included.

Disposition of all subjects who participate in substudy will be summarized by treatment groups, age groups (6 - 10 years, and 11 – 17 years) and overall including:

- Number of subjects who participated in substudy
- Number of subjects vaccinated on Day 1
- Number of subjects vaccinated on Day 85
- Number of subjects who are also in the following analysis sets:
 - Safety Analysis Set
 - Immunogenicity Analysis Set

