8.4. Analyses of Endpoints for the Optional Substudy

8.4.1. Analysis of Colonization Endpoints

Colonization summary tables will be produced based on the sample type (mid-turbinate swab and nasopharyngeal swab).

The analyses in this section of the colonization substudy will be based on the PP immunogenicity analysis set but include only subjects who are enrolled in the optional open-label substudy. A sensitivity analysis will be conducted using the Immunogenicity Analysis Set but include only subjects who are enrolled in the optional open-label substudy.

To assess if prior BPZE1 induced mucosal immunity substantially reduces colonization at Days 92 and 99, the proportion of subjects with colonization at Day 92 or Day 99 will be analyzed. The 2-sided 95% CI in the proportion of subjects with colonization at either Day 92 or Day 99 (*B. pertussis* culture or PCR) will be calculated using Agresti-Coull method and summarized by treatment groups (BPZE1, BPZE1 + Boostrix, BPZE1 and BPZE1 + Boostrix, Boostrix control). The likelihood ratio chi-square test will be used to compare the proportions between treatment groups.

Separate relative risks, which are defined as the ratio of two treatment group proportions, will be calculated for 1) BPZE1 vs. BPZE1 + Boostrix; 2) BPZE1 vs. Boostrix control; 3) BPZE1 + Boostrix vs. Boostrix control; 4) BPZE1 and BPZE1 + Boostrix vs. Boostrix control. The CI for relative risk will be computed using the likelihood ratio method.

The relative risk reduction (RRR) is defined as $RRR (\%) = (1 - RR) \times 100$. The CI for the RRR will be obtained by transforming the CI for the relative risk using $(1 - UL, 1 - LL)$, where UL denotes the upper limit of the CI for the RR and LL denotes the lower limit of the CI for the RR.

The hypotheses for the primary endpoint are:

H0: RRR $\leq 0\%$

HI: RRR $> 0\%$

Rejection of the null hypothesis demonstrates a statistically significant vaccine effect, (i.e., LL of the CI $> 0\%$), and will be considered to meet the pre-specified study success criterion.

Colonization at Day 8 safety lead-in group will be analyzed to determine specimen type. Colonization at Day 29 or Day 85 will be analyzed for clearance of BPZE1.

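### SAP 4.4 imputes colonisation on substudy consent rather than on challenge, conflicts with the per-protocol removal rule in 4.3.4, and pools a risk difference although 8.4.1 judges success on the relative risk reduction

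*SAP*

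**What the plan says.** **Who is imputed.** SAP 4.4 covers the both-days-missing case as follows: "When subjects drop out before they visit on Day 92 but consent to the substudy". For these subjects, "Status of being positive or negative for a given day will be imputed using fully conditional specification multiple imputation". The conventions are stated for summaries and analyses generally, and no analysis set is named. SAP 3.1 says that "enrolled subjects may elect to participate at any time from the day of enrolment through Day 85".

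**Who is removed.** SAP 4.3.4 lists, among the per-protocol (PP) exclusions, that for the substudy "missing Day 92 and Day 99 cultures will be removed from the Colonization endpoint". SAP 8.4.1 then states: "The analyses in this section of the colonization substudy will be based on the PP immunogenicity analysis set". The Immunogenicity Analysis Set is used for a sensitivity analysis. Both are limited to subjects enrolled in the substudy.

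**What is pooled.** Step 2 of the imputation procedure sends each of the 50 completed data sets to 8.4.1. Step 3 says the "difference in response proportion and its standard errors, will then be combined per Rubin's rule".

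**What 8.4.1 produces.** It gives Agresti-Coull intervals for single proportions, a likelihood ratio chi-square test, relative risks (RR), and RRR = (1 − RR) × 100. For the interval, "The CI for relative risk will be computed using the likelihood ratio method", and its limits are transformed to the RRR scale. Success is a lower RRR limit above 0%.

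**The concern.** These three rules determine the denominator and the interval for colonisation, and they do not fit together.

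- The endpoint is colonisation after the Day 85 challenge. A child who consents early and leaves before Day 85 has no such outcome. It is undefined rather than missing, and imputation has nothing to recover.
- A subject with neither culture is removed under 4.3.4 and imputed under 4.4. A programmer must choose, and the SAP does not say which rule takes precedence.
- Where imputation is used, the quantity that step 3 combines is not one that 8.4.1 outputs, and it is not the one on which the criterion is stated.

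The substudy has at most 120 subjects and no stated power for colonisation. A few subjects per arm can move a lower limit that lies near zero.

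**Working it through.** The plan states no sample size, power or rate for colonisation, so it has no figure to reproduce. The check is a comparison of texts, some algebra, and one illustration on assumed rates.

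**1. Can an unchallenged subject meet the imputation trigger?** The trigger is consent plus dropout before Day 92. Consent can be given from enrolment. The Immunogenicity Analysis Set needs a baseline and one post-vaccination sample, so a Day 29 sample is enough and the set does not screen out someone who left before Day 85. SAP Section 5 (Subject Disposition) has a line for substudy participation and a separate line, "Number of subjects vaccinated on Day 85", so the two counts are allowed to differ. The wording therefore includes such subjects.

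**2. Remove or impute?**

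| Both cultures missing | Rule |
|---|---|
| SAP 4.3.4, PP set | removed from the endpoint |
| SAP 4.4, no set named | multiply imputed |
| SAP 8.4.1 | main analysis on the PP set |

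If 120 subjects split evenly (assumed), there are 120/3 = 40 per arm. With 10% missing both days (assumed), the denominator is 36 or 40 depending on the rule.

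**3. Does the pooled risk difference (RD) give the RRR?** Let p1 be the BPZE1 proportion and p0 the control proportion. RD = p1 − p0 and RRR = 1 − p1/p0. For RD = −0.30:

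| p1 v p0 | RRR |
|---|---|
| 0.1 v 0.4 | 1 − 0.1/0.4 = 75.0% |
| 0.2 v 0.5 | 1 − 0.2/0.5 = 60.0% |
| 0.4 v 0.7 | 1 − 0.4/0.7 = 42.9% |
| 0.6 v 0.9 | 1 − 0.6/0.9 = 33.3% |

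One RD corresponds to many RRRs, so the pooled RD fixes neither the RRR nor its interval. A likelihood ratio interval also supplies no standard error for Rubin's rules. The null is shared, however: for p0 > 0, RD < 0 exactly when RRR > 0.

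**4. Illustration (all rates assumed).** There are 40 consented per arm, 4 per arm missing both days, control near 0.9 and BPZE1 near 0.3 to 0.7, rounded to whole subjects. Imputation used 50 within-arm beta-binomial draws, as a stand-in for the SAP's logistic model and without the age covariate. Var(ln RR) = (1 − p1)/(n·p1) + (1 − p0)/(n·p0), and total variance = mean within-variance + (1 + 1/50) × between-variance.

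| Observed | RRR, removal, likelihood ratio CI | RRR, imputation, pooled ln(RR) |
|---|---|---|
| 11/36 v 32/36 | 65.6% (46.4 to 80.8) | 65.4% (42.7 to 79.1) |
| 18/36 v 32/36 | 43.8% (23.1 to 62.1) | 43.8% (20.1 to 60.4) |
| 22/36 v 32/36 | 31.2% (10.5 to 50.3) | 31.0% (8.1 to 48.2) |
| 25/36 v 32/36 | 21.9% (1.3 to 40.9) | 21.9% (0.2 to 38.9) |

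The gap in lower limits mixes two things: imputation, and a Wald-type interval in place of the likelihood ratio one. In the last row the pooled RD is −0.195 (−0.376 to −0.014), p = 0.035. Pooled ln(RR) gives p = 0.048. The conclusion is the same, but the figures are not identical.

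**The case against.** Three stronger readings are tempting, and the documents do not support them.

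- **That the RRR inference cannot be obtained at all.** The pooled RD tests the same null. Under the 4.3.4 removal rule, 8.4.1 yields its likelihood ratio RRR interval directly, provided no one-day gap needs imputation. The Agresti-Caffo difference can also be reached through Protocol 7.4.4 and 7.4.2. However, the SAP governs where the two differ, and 4.4 points to 8.4.1, which computes no difference. What stands is that no pooled RRR and interval are specified after imputation.
- **That imputed values for unchallenged children enter the main result.** Under 4.3.4 they are removed from the PP endpoint. They would enter only if 4.4 overrides 4.3.4, and the SAP does not say that it does.
- **That the SAP sets out to impute unchallenged children.** It says all participants receive BPZE1 on Day 85, and consent and eligibility are reviewed before that dose. Dropping out before Day 92 may have been meant for Day 85 attendees only. The defect is a missing restriction, and it remains because the text uses consent.

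It can also be argued that 4.3.4 and 4.4 are compatible if both-missing imputation serves only the sensitivity analysis. That is sensible, but nothing in the SAP says it.

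The stakes are limited. The secondary colonisation objective is descriptive, percent reduction is exploratory, and SAP 8.1 rests study success on the two S-IgA comparisons, even though 8.4.1 uses success language. In the four assumed scenarios the point estimates barely move and every lower limit stays above zero.

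**Conclusion.** The point holds as three defects in stated rules: the trigger is consent rather than challenge, removal in 4.3.4 conflicts with imputation in 4.4, and step 3 pools a quantity that 8.4.1 neither computes nor uses for its criterion.

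The size of the effect is unknown, because the documents give no colonisation or missingness rates. On the assumed rates the choice of rule moves the lower RRR limit by 1.1 to 3.7 percentage points (1.3 − 0.2 in the smallest case, 46.4 − 42.7 in the largest) and does not change the conclusion. It matters only where the limit lies close to zero. The change should be made before database lock, but it does not touch the primary result.

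**What to change.** Amend SAP 4.3.4, 4.4 and 8.4.1 together:

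1. Restrict the colonisation analysis, and any imputation, to substudy subjects who received the Day 85 BPZE1.
2. State that subjects missing both cultures are removed in the PP analysis and multiply imputed only in the Immunogenicity-set sensitivity analysis.
3. Keep the existing multiple imputation rule for Day 92 missing with Day 99 negative, and state that it applies in both sets. Otherwise these subjects stay in the PP set with no rule.
4. Wherever multiple imputation is used, replace the risk difference in step 3 with ln(RR) and its standard error, pooled by Rubin's rules. Report RRR = 1 − exp(pooled ln RR) with back-transformed limits, and state a zero-cell rule in advance.
5. Keep the likelihood ratio interval when no value is imputed.

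The cost is SAP wording and programming, with no change to conduct or sampling. One small drawback is that a Wald-type interval replaces the likelihood ratio interval in the imputed analyses.
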